**Table 9-2 Prohibited Medications**

Medication	Timing of Restriction		Rationale
	Start of Restriction	End of Restriction	
Moderate and strong CYP3A inducers	None allowed within 14 days before the first dose of the study drug on Day -28	None allowed through completion of study participation	VX-445, TEZ, and IVA are metabolized extensively via CYP3A4. Therefore, use of moderate and strong inducers of CYP3A and moderate and strong inhibitors of CYP3A, which have the potential to alter the exposure of VX-445, TEZ, or IVA, will be prohibited.
Moderate and strong CYP3A inhibitors (except ciprofloxacin) a	None allowed within 14 days before the first dose of the study drug on Day -28	None allowed through completion of study participation	
Non-Vertex CFTR modulators (investigational or approved)	None allowed within 28 days or 5 terminal half-lives (whichever is longer) before screening	None allowed through completion of study participation	These agents may confound the results of this study.
Vertex CFTR modulators (investigational or approved), except for study drugs	None allowed from the first dose of study drug on Day -28	None allowed until after the last dose of study drug	These agents may confound the results of this study.

CYP: cytochrome P450; IVA: ivacaftor; TEZ: tezacaftor

a Ciprofloxacin is not a moderate CYP3A inhibitor on the basis of results of a drug-drug interaction study conducted with IVA, a sensitive CYP3A substrate (Kalydeco [ivacaftor] US Package Insert).

## 9.5 Prior and Concomitant Medications

Information regarding prior and concomitant medications, including CF medications, other medications, and herbal and naturopathic remedies, will be collected from each subject's source documentation for medications taken within 56 days before the Screening Visit through completion of study participation, as defined in Section 9.1.7.

For subjects who are screened, but are not subsequently randomized into the Treatment Period, details of prior medication will be documented only in the subjects' source documents.

- Subjects should remain on a stable treatment regimen for their CF from 28 days before the TEZ/IVA Run-in Period/Day -28 through completion of study participation. Stable treatment regimen is defined as the current treatment regimen for CF that subjects have been following for at least 28 days before the TEZ/IVA Run-in Period/Day -28. Subjects may remain on Vertex CFTR modulators (investigational or approved) during the Screening Period and may transition directly to the TEZ/IVA Run-in/Day -28 without a washout (Table 9-2). Subjects

should not initiate long-term treatment with new medication from 28 days before the TEZ/IVA Run-in Period/Day -28 through completion of study participation. Guidelines for stable treatment regimens for CF are as follows:

- o Subjects who are taking inhaled tobramycin or other chronically inhaled antibiotics should remain on that regimen throughout the study.
  - o Subjects who cycle onto and off of an inhaled antibiotic should continue on their prior schedule. The timing of the first dose of study drug on the Day 1 Visit should be synchronized as closely as possible (e.g., not more than  $\pm 3$  days) to the first day in the cycle onto the inhaled antibiotic.
  - o Subjects who alternate between 2 different inhaled antibiotics should remain on the same cycling schedule during the study. The timing of the first dose of study drug on the Day 1 Visit should be synchronized as closely as possible (e.g., not more than  $\pm 3$  days) to the first day in the cycle onto 1 of the inhaled antibiotics.
- Subjects may receive doses of prednisone or prednisolone of up to 10 mg/day chronically, or up to 60 mg daily for up to 5 days.
  - VX-445 may inhibit OATP1B1 and OATP1B3, which may increase the exposure of medicinal products that are substrates for these transporters. Substrates such as statins, glyburide, nateglinide, and repaglinide should be used with caution.
  - IVA is a weak inhibitor of P-glycoprotein (P-gp). Administration of IVA may increase systemic exposure of medicinal products that are sensitive substrates of P-gp, which may increase or prolong their therapeutic effect and adverse reactions. Digoxin or other substrates of P-gp with a narrow therapeutic index, such as cyclosporine, everolimus, sirolimus, and tacrolimus, should be used with caution and appropriate monitoring.
  - IVA may inhibit CYP2C9; therefore during coadministration with warfarin, additional monitoring of the international normalized ratio is recommended. Other medicinal products that are CYP2C9 substrates for which exposure may be increased include glimepiride and glipizide; these should be used with caution.
  - Information about bronchodilator use during the study will be collected and documented. Subjects who are using a bronchodilator must have their spirometry assessments performed according to the guidelines provided in Section [11.4.2](#).

## 9.6 Administration

### 9.6.1 Dosing

Study drug will be administered orally. All subjects will receive the same number of tablets each day to maintain the blind. Additional information is provided in the Pharmacy Manual.

Study drug should be administered with a fat-containing meal or snack, such as a standard “CF” meal or snack or a standard meal.

1. It is recommended that the dose be taken within 30 minutes of the start of the meal or snack.
2. Study drug will be administered as fixed-dose combination (FDC) tablet(s) (e.g., 2 VX-445/TEZ/IVA or matching placebo tablets; 1 TEZ/IVA or matching placebo

tablet) in the morning and as 1 IVA tablet in the evening. For each subject, doses of study drugs should be taken at approximately the same time ( $\pm 2$  hours) each day.

3. On days of scheduled visits, the morning dose of study drug will be administered at the site after predose assessments have been completed. A meal or snack will be provided by the site for the morning dose of study drug.
4. If a subject's scheduled visit is to occur in the afternoon, the following guidelines must be used:
  - If the dose in the clinic will be within 6 hours of the subject's scheduled morning dose, the subject should withhold their morning dose of study drug and the morning dose will be administered in the clinic.
  - If the dose in the clinic will be more than 6 hours after the subject's scheduled morning dose, the subject should take the morning dose of study drug at home.
5. Subjects will be instructed to bring all used and unused materials associated with the study drug to the site; study drug will be dispensed at each visit, as appropriate.

### **9.6.2 Missed Doses**

If 6 hours or less have passed since the missed morning or evening dose, the subject should take the missed dose as soon as possible and continue on the original schedule.

**Morning dose:** If more than 6 hours have passed since the missed morning dose, the subject should take the missed dose as soon as possible and should not take the evening dose.

**Evening dose:** If more than 6 hours have passed since the missed evening dose, the subject should not take the missed dose. The next scheduled morning dose should be taken at the usual time.

Morning and evening doses should not be taken at the same time.

### **9.7 Dose Modification for Toxicity**

No dose modifications for toxicity are allowed. Treatment may be interrupted; if any unacceptable toxicity arises, individual subjects will discontinue dosing.

### **9.8 Study Drug Interruption and Stopping Rules**

In subjects who have interrupted study drug for  $>72$  hours for any reason, the investigator should resume study drug only after a thorough investigation of the cause for interruption. The investigator should evaluate the subject's clinical stability and only resume drug after the subject is clinically stable and there is no comorbidity or condition that, in the opinion of the investigator, might confound the results of the study or pose an additional risk in administering study drug to the subject.

The medical monitor should be notified of an interruption of study drug that lasts  $>72$  hours for any reason and of the resumption of study drug after such interruption. The medical monitor should be notified of any plan to discontinue study drug.

#### **9.8.1 Liver Function Tests**

The central laboratory will notify the medical monitor of instances of ALT or AST  $>3 \times$  ULN in association with total bilirubin  $>2 \times$  ULN that are derived from centrally submitted samples.

Subjects with new treatment-emergent ALT or AST elevations of  $>3 \times \text{ULN}$ , with or without total bilirubin  $>2 \times \text{ULN}$ , must be followed closely, including confirmatory testing performed by the central laboratory within 48 to 72 hours of the initial finding and subsequent close monitoring of ALT, AST, and bilirubin levels, as clinically indicated.

If a subject cannot return to the site for central laboratory confirmatory testing, a local laboratory may be used. Local laboratory results must be reported immediately to the medical monitor, and the subject must have the tests repeated and sent to the central laboratory as soon as possible (ideally within 48 to 72 hours).

Study drug administration **must be interrupted** immediately (before confirmatory testing) if any of the following criteria are met:

- ALT or AST  $>8 \times \text{ULN}$
- ALT or AST  $>5 \times \text{ULN}$  for more than 2 weeks
- ALT or AST  $>3 \times \text{ULN}$ , in association with total bilirubin  $>2 \times \text{ULN}$  and/or clinical jaundice

A thorough investigation of potential causes should be conducted, and the subject should be followed closely for clinical progression.

Study drug administration **must be discontinued** if the following criterion is met:

- Subsequent ALT or AST values confirm the initial elevation that satisfied the interruption rule (above), and no convincing alternative etiology (e.g., acetaminophen use, viral hepatitis, alcohol ingestion) is identified, regardless of whether transaminase levels have improved

All subjects in whom treatment is discontinued for elevated transaminases (and bilirubin, as applicable) should have these levels monitored closely until levels normalize or return to baseline.

If an alternative, reversible cause of transaminase elevation with or without increased bilirubin or clinical jaundice has been identified, study drug administration may be resumed once transaminases return to baseline or are  $\leq 2 \times \text{ULN}$ , whichever is higher. Regardless of the duration of interruption, the medical monitor should be notified before resumption of study drug. Upon resumption of study drug, transaminases and bilirubin should be assessed weekly for 4 weeks. If a protocol-defined transaminase elevation interruption threshold recurs within 4 weeks of rechallenge with the study drug (with confirmation of the initial elevation by repeat testing within 48 to 72 hours), then the study drug must be permanently discontinued, regardless of the presumed etiology.

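### The liver-test restart rule in Protocol Section 9.8.1 covers subjects with raised bilirubin or jaundice but sets a recovery limit for transaminases only

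*Protocol*

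**What the plan says.** Section 9.8.1 of the Protocol lists three criteria that force immediate interruption of study drug:

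- ALT or AST above 8 x ULN;
- ALT or AST above 5 x ULN for more than 2 weeks;
- ALT or AST above 3 x ULN in association with total bilirubin above 2 x ULN "and/or clinical jaundice".

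If repeat values confirm the elevation and no convincing alternative cause is found, drug must be stopped for good. If an alternative, reversible cause is found, the restart sentence applies: "with or without increased bilirubin or clinical jaundice has been identified, study drug administration may be resumed once transaminases return to baseline". A level of at most 2 x ULN also qualifies, and the higher of the two limits counts.

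Three further conditions surround a restart in the same section:

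- Notice comes first: "Regardless of the duration of interruption, the medical monitor should be notified before resumption of study drug".
- ALT, AST and bilirubin are then checked each week during the first 4 weeks back on drug.
- A recurrence rule follows: "If a protocol-defined transaminase elevation interruption threshold recurs within 4 weeks of rechallenge with the study drug", and repeat testing confirms it, drug is permanently discontinued whatever the presumed cause.

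Section 9.8 adds a general check for any interruption longer than 72 hours: the investigator should "only resume drug after the subject is clinically stable and there is no comorbidity or condition that, in the opinion of the investigator", could cloud the findings or put the subject at added risk. Section 9.7 says that "if any unacceptable toxicity arises, individual subjects will discontinue dosing", and Section 9.9 lets the investigator or the sponsor withdraw a subject from treatment for safety at any time.

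**The concern.** The restart sentence names raised bilirubin and jaundice as situations that it governs, and then asks only about transaminases. This is more than a missing detail: a rule is stated for these subjects, and it can be satisfied without looking at the second half of the finding that stopped their drug.

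The protocol treats that second half as important elsewhere. The combination of ALT or AST above 3 x ULN with total bilirubin above 2 x ULN prompts central-laboratory notice to the medical monitor and forces interruption (Section 9.8.1), and the SAP counts it as a threshold event of its own (Appendix E, Table 12-3). For subjects taken off drug permanently, both measures are followed: those "discontinued for elevated transaminases (and bilirubin, as applicable) should have these levels monitored closely until levels normalize or return to baseline". Restart, where the subject is exposed again, has no matching condition.

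What is at stake is the safety of a small number of subjects. An investigator could reasonably take the one number given as sufficient.

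**Working it through.** The plan states no figure to reproduce. The check sets the liver rules side by side and then applies the restart rule to assumed values.

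**Step 1. The limits (multiples of ULN).**

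| Step | ALT or AST | Total bilirubin | Clinical jaundice |
|---|---|---|---|
| Interruption, criteria 1 and 2 | >8, or >5 for more than 2 weeks | not used | not used |
| Interruption, criterion 3 | >3, and one of the next two | >2 | present |
| Restart, reversible cause found | at most the higher of baseline and 2 | no limit | no condition |
| First 4 weeks after restart | weekly test; stop on confirmed recurrence of an interruption threshold | weekly test; acts only through criterion 3 | acts only through criterion 3 |
| After permanent discontinuation | followed to normal or baseline | followed likewise, as applicable | not mentioned |

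**Step 2. The restart test.** It is met when ALT and AST are at most max(baseline, 2). Bilirubin and jaundice do not enter it.

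**Step 3. Example A** (assumed values; baseline ALT at most 2; AST at or below ALT). Drug is interrupted at ALT 3.5 and bilirubin 5, since 3.5 > 3 and 5 > 2. A reversible cause is found. Later ALT is 1.9 and bilirubin 4.

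- Restart test: max(baseline, 2) = 2 and 1.9 ≤ 2, so it is met.
- Bilirubin: 4 > 2, so it is still in the range used in criterion 3.
- Criterion 3 as a whole: 1.9 is not above 3, so it no longer applies.

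With bilirubin at 2.1, 3, 4 or 5 on that day the answer is the same, because the restart test does not use bilirubin.

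**Step 4. Example B** (assumed values; same baseline and AST assumptions). Drug is interrupted for ALT 9 with normal bilirubin (criterion 1, 9 > 8). Bilirubin rises to 3 during the interruption and ALT falls to 1.9. The restart test is met (1.9 ≤ 2) with bilirubin at 3. Bilirubin did not cause this interruption, so a remedy limited to criterion 3 would miss the case.

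**Step 5. Search for a limit elsewhere.**

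| Control | Bilirubin or jaundice limit for restart? |
|---|---|
| Section 9.8 stability and added-risk check | None; investigator's opinion, only after more than 72 hours |
| Medical monitor, Section 9.8.1 | None; notice is required, approval is not |
| Weekly tests, Section 9.8.1 | None; they begin after re-exposure |
| Rechallenge stop, Section 9.8.1 | None; it needs ALT or AST to cross an interruption threshold again |
| Sections 9.7 and 9.9 | None; no value given |

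The remaining bilirubin limits are the screening exclusion in Section 8.2 and the SAP's summary categories. Neither governs restart.

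**The case against.** The strongest reply is that bilirubin never acts alone in Section 9.8.1. Criterion 3 is a conjunction, and once transaminases are at or below 2 x ULN it is no longer met. A subject already on drug with ALT 1.9 x ULN and bilirubin 4 x ULN would meet no interruption criterion, so a bilirubin limit would make restart stricter than continuation. The premise is right, but the conclusion does not count against the limit, because the protocol already does this for transaminases. Without raised bilirubin or jaundice, a subject may continue at up to 8 x ULN (above 5 x ULN for no more than 2 weeks), yet must be at baseline or at most 2 x ULN to restart.

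The second reply is that the dangerous case is already covered. Restart is permitted, not required; a reversible cause must have been identified; and the medical monitor is told first. Most such interruptions should outlast 72 hours, since confirmatory testing alone is timed at 48 to 72 hours (an inference), so the Section 9.8 check would usually apply, and persistent jaundice is just what it should catch. After restart, a subject whose bilirubin is still above 2 x ULN meets criterion 3 again as soon as ALT or AST passes 3 x ULN, and confirmed recurrence within 4 weeks ends treatment. All of this stands and keeps the point small. It does not supply a limit: the same judgement controls apply to transaminases, and the protocol still gave those a number.

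A reader might infer more than the text supports:

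- *That a subject could restart at some multiple of the bilirubin trigger.* There is no stand-alone bilirubin trigger, so such a ratio has no meaning here.
- *That exceeding the screening limit for bilirubin (2 x ULN or more) proves the rule unsafe.* Entry limits are not treatment limits in this protocol. ALT or AST of 3 x ULN or more excludes at screening, but does not by itself interrupt a treated subject.
- *That drug could be restarted after unexplained liver injury.* A confirmed elevation without a convincing alternative cause requires discontinuation.

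**Conclusion.** The point holds as a gap in a stated safety rule, at low severity. The restart sentence covers subjects with raised bilirubin or jaundice, and its only recovery limit is for transaminases. It can be met with bilirubin above 2 x ULN or with jaundice still present, and no other provision sets a limit for that decision, which is left to the investigator's judgement and to any sponsor action after notice.

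The documents give no frequency. The case is expected to be rare, because it needs an identified reversible cause together with bilirubin or jaundice that recovers more slowly than transaminases. Both worked examples use assumed values and show only what the wording permits. Endpoints, power and type I error are unaffected. The section does not contradict itself; this is a cheap improvement to its wording.

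**What to change.** Amend the restart sentence in Section 9.8.1. A subject who had total bilirubin above 2 x ULN or clinical jaundice at or during the interruption, whichever criterion caused it, may resume only when all three conditions hold:

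1. transaminases are at baseline or at most 2 x ULN, whichever is higher;
2. total bilirubin is at baseline or at most 2 x ULN, or meets a stricter limit set by the sponsor's medical team;
3. clinical jaundice has resolved.

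Keep every other condition: the reversible cause, notice to the medical monitor, the Section 9.8 check, the weekly tests and the rechallenge stop. The documents give no restart value for bilirubin. The 2 x ULN figure is proposed because it complements the bilirubin limb of criterion 3. Neither worked example could then restart (4 > 2 and 3 > 2), assuming a baseline bilirubin of at most 2 x ULN.

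**Cost.** This is a protocol amendment under Section 13.2.3: agreement of the investigator and the sponsor, regulatory submission, and ethics committee notification if the change is held to affect safety significantly. No new test is needed, since total bilirubin is in the serum chemistry panel (Table 11-1) and Section 9.8.1 already calls for monitoring it in these subjects. An occasional subject would stay off drug longer. Each extra week is 7/168 = 4.2% of the 24-week Treatment Period for that subject, and a subject already in the Full Analysis Set stays in it as randomized.

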### **9.8.2 Rash**

Individuals who develop a generalized rash will be monitored closely. Study drug dosing should be interrupted if a subject develops a generalized rash of Grade 3 or higher, or a rash that is considered a serious adverse event (SAE). The investigator will notify the medical monitor of any rash that results in interruption of study drug, is Grade 3 or higher (Section 13.1.1.4), or is an SAE. Investigators should consider additional evaluation including laboratory testing (e.g., complete blood count with differential, liver function tests), photographs of the rash, and dermatology consultation. The investigator may consider resumption of study drug if considered clinically appropriate.

## 9.9 Removal of Subjects

Subjects may withdraw from the study at any time at their own request. Subjects may be withdrawn from study drug treatment at any time at the discretion of the investigator or Vertex for safety, behavior, noncompliance with study procedures, or administrative reasons. If a subject has been withdrawn from study drug treatment, the subject will continue to be followed, provided that the subject has not withdrawn consent (and assent, as applicable).

In addition, a subject must be discontinued from study drug treatment if the subject meets any of the following criteria:

- Has a screening *CFTR* genotype that does not confirm study eligibility if a previous *CFTR* genotype laboratory report was used to establish eligibility. These subjects must be discontinued from the study (Section 8.1)
- Meets any of the stopping (discontinuation) criteria (Section 9.8)
- Becomes pregnant (Section 11.5.7.2)

Subjects who discontinue study drug treatment should return for study assessments, as noted in Section 9.1.5.2.

If a subject does not return for a scheduled visit, reasonable effort will be made to contact the subject. In any circumstance, reasonable effort will be made to document subject outcome. The investigator will inquire about the reason for withdrawal, request that the subject return all unused investigational product(s), request that the subject return for an ETT Visit and Safety Follow-up Visit, if applicable (see Section 9.1.5), and follow up with the subject regarding any unresolved AEs.

If the subject withdraws consent or assent for the study, no further assessments will be performed. Vertex may retain and continue using the study data and samples after the study is over, and may use the samples and information in the development of the study compound, and for other drugs and diagnostics, in publications and presentations, and for education purposes. If the subject withdraws from the study, the study data and samples collected will remain part of the study. A subject will not be able to request the withdrawal of his/her information from the study data. A subject may request destruction of the samples collected from him/her during the study as long as those samples can be identified as his/her samples.

